10. EVALUATION OF QUALITY OF LIFE

10.1 Quality of Life Scoring

10.1.1 EORTC QLQ-C30 and QLQ-CR29

The European Organization for Research and Treatment of Cancer (EORTC) QLQ-C30 (version 3.0) ([Aaronson et. al., 1993](#)) supplemented by the colorectal cancer module (QLQ-CR29) ([Whistance et. al., 2009](#)) are validated instruments and will be used to measure quality of life and assess symptoms and side effects of treatment and their impact on everyday life.

The QLQ-C30 is composed of 5 multi-item functional scales (physical, role, social, emotional and cognitive functioning), a global health status/QoL scale, and 9 symptom scales (fatigue, nausea/vomiting, pain, financial impact, appetite loss, diarrhea, constipation, sleep disturbance and dyspnea).

The colorectal cancer module (QLQ-CR29) incorporates functional scales to assess body image, anxiety, weight, and sexual interest. The QLQ-CR29 also includes symptom scales to assess urinary frequency, blood and mucus in stool, stool frequency, urinary incontinence, dysuria, abdominal pain, buttock pain, bloating, dry mouth, hair loss, taste, flatulence, fecal incontinence, sore skin, embarrassment, stoma care problems, impotence, and dyspareunia.

Most items are answered on a 4-point scale (i.e., 1=Not at all, 2=A Little, 3=Quite a Bit, 4=Very Much) except the items contributing to the global health status/QoL, which have a 7-point scale (1=Very Poor to 7=Excellent). Raw scores (reported on eCRFs) will be transformed using a linear transformation to standardize the results so that scores for each functional and symptom scale range from 0 to 100.

The calculation for scoring these scales is the same in all cases ([Fayers et. al., 2001](#))

1. Calculate the average of the items that contribute to the scale; this is the raw score.

2. Use a linear transformation to standardize the raw score, so that scores range from 0 to 100; a higher score represents a higher ("better") level of functioning, or a higher ("worse") level of symptoms.

Calculations for raw score and linear transformation are as follows:

In practical terms, if items I_1, I_2, \dots, I_n are included in a scale, where n is number of items in the scale, the procedure is as follows:

Raw score

$$RS \text{ (Raw Score)} = (I_1 + I_2 + I_3 + \dots + I_n)/n$$

Linear transformation

Apply the linear transformation to 0-100 to obtain the score S ,

$$\text{Functional scales: } S = \{(RS - 1)/\text{range}\} \times 100$$

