$$\text{Symptom scales / items: } S = \{(RS - 1)/\text{range}\} \times 100$$

$$\text{Global health status / QoL: } S = \{(RS - 1)/\text{range}\} \times 100$$

Range is the difference between the maximum possible value of RS and the minimum possible value.

The raw score and linear transformed score will be calculated when at least 50% of the items from the scale have been answered. Otherwise, the score will be missing.

The structure of this questionnaire and scoring are presented in [Table 6](#) and [Table 7](#).

Table 6: Scoring for QLQ-C30 version 3.0

Scale	Scale abbreviation	Number of items	Range	Item Number
Global health status / QoL				
Global health status/QoL	QL	2	6	29, 30
Functional scales				
Physical functioning	PF	5	3	1 to 5
Role functioning	RF	2	3	6, 7
Emotional functioning	EF	4	3	21 to 24
Cognitive functioning	CF	2	3	20, 25
Social functioning	SF	2	3	26, 27
Symptom scales / items				
Fatigue	FA	3	3	10, 12, 18

Nausea and vomiting	NV	2	3	14, 15
Pain	PA	2	3	9, 19
Dyspnoea	DY	1	3	8
Insomnia	SL	1	3	11
Appetite loss	AP	1	3	13
Constipation	CO	1	3	16
Diarrhea	DI	1	3	17
Financial difficulties	FI	1	3	28

Table 7: Scoring for QLQ-CR29

Scale	Scale abbreviation	Number of items	Range	Item Number
Functional scales				
Body Image	BI	3	3	15-17
Anxiety	ANX	1	3	13
Weight	WEI	1	3	14
Sexual interest (men)	SEXM	1	3	26 ^{a,c}
Sexual interest (women)	SEXW	1	3	28 ^{a,c}
Symptom scales / items				
Urinary frequency	UF	2	3	1,2
Blood and mucus in stool	BMS	2	3	8,9
Stool frequency	SF	2	3	22,23 ^b
Urinary incontinence	UI	1	3	3
Dysuria	DY	1	3	4
Abdominal pain	AP	1	3	5
Buttock pain	BP	1	3	6
Bloating	BF	1	3	7
Dry mouth	DM	1	3	10
Hair loss	HL	1	3	11
Taste	TA	1	3	12
Flatulence	FL	1	3	19 ^b
Fecal incontinence	FI	1	3	20 ^b
Sore skin	SS	1	3	21 ^b
Embarrassment	EMB	1	3	24 ^b
Stoma care problems	STO	1	3	25
Impotence	IMP	1	3	27 ^a
Dyspareunia	DSY	1	3	29 ^a

^a Note that items 26 and 27 are for men only, and items 28 and 29 are for women only. Thus, these questions will be answered only by a subset of patients.

^b When scoring scales or single items that include questions 19 to 24, use the answer to question 18: 'Do you have a soma bag (colostomy/ileostomy)? Yes/No to ensure that answers are taken from the relevant box of questions

^c In order for the two sexual interest scales to be interpreted as functional scales (i.e. a higher score is better), they should be scored according to the symptom scale algorithm.

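### SAP 10.1.1 fixes the EORTC raw-score divisor at the full item count yet scores half-answered scales; taken literally, partial scales shift by about 6.7 to 66.7 points

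*SAP*

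**What the plan says.** SAP 10.1.1 describes the raw score twice. In words, step 1 reads: "Calculate the average of the items that contribute to the scale; this is the raw score". The formula then gives RS = (I_1 + ... + I_n)/n, "where n is number of items in the scale, the procedure is as follows". Tables 6 and 7 fix that number for each scale, for example 5 for physical functioning, 3 for fatigue and 2 for global health.

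The transformation is S = {(RS − 1)/range} × 100, printed identically for functional scales, symptom scales and global health. On range, the SAP says: "Range is the difference between the maximum possible value of RS and the minimum possible value". Tables 6 and 7 give 3 for the four-point items and 6 for global health. The stated aim is that "scores for each functional and symptom scale range from 0 to 100".

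For incomplete scales the rule is: "The raw score and linear transformed score will be calculated when at least 50% of the items from the scale have been answered". Below that threshold, "Otherwise, the score will be missing". No separate divisor is given for a scale that passes the threshold with items missing.

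**The concern.** The formula describes a complete scale, and the half rule orders its use on incomplete ones. A programmer who sums the available items and divides by the tabulated n follows the printed definition. That program in effect gives each blank the value 0, although the lowest response code is 1.

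The transformed scores feed the summaries of absolute values and changes from baseline. In Part 2 they also feed a two-sided Wilcoxon rank sum test at 0.05 (SAP 10.2). The questionnaires are completed only at baseline, End of Study/Early Termination and Safety Follow-up (Protocol 20.2, Tables 3 to 5), so each subject contributes few scores. Part 2 plans 66 subjects, 22 of them controls. On a symptom scale, a downward shift makes a subject who skipped an item look less symptomatic than the answers given.

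**Working it through.** **Inputs.** From SAP 10.1.1: items are coded 1 to 4, or 1 to 7 for global health; range is 3 or 6; n per scale is taken from Tables 6 and 7; the half rule is as quoted. Let m be the number of items answered and M their mean.

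**Plan's own figure first.** With all items answered, RS runs from 1 to 4 (or 1 to 7). S therefore runs from (1 − 1)/3 × 100 = 0 to (4 − 1)/3 × 100 = 100, and likewise for global health with range 6. The stated 0 to 100 is reproduced for complete scales.

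**Two ways to score a partial scale.**
- Fixed divisor: RS = (sum of answered items)/n = M × m/n.
- Mean of answered items: RS = (sum of answered items)/m = M.

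The difference in S, fixed divisor minus mean, is −M × (1 − m/n)/range × 100. Since M is at least 1 and m is less than n, it is always negative under the printed formulas.

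**Examples.**
- Two-item symptom scale, one item answered 4: fixed (4/2 − 1)/3 × 100 = 33.3; mean (4 − 1)/3 × 100 = 100.
- Fatigue, two of three items answered 3: fixed (6/3 − 1)/3 × 100 = 33.3; mean 66.7.
- Global health, one of two items answered 7: fixed (3.5 − 1)/6 × 100 = 41.7; mean 100.
- Physical functioning, three of five items answered 1: fixed (0.6 − 1)/3 × 100 = −13.3; mean 0.
- Physical functioning, four of five items answered 1: fixed (0.8 − 1)/3 × 100 = −6.7; mean 0.

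**All answer patterns that pass the half rule.**

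| Scale | n | m | S with fixed divisor | Shift against mean of answered items |
|---|---|---|---|---|
| Two-item scales, range 3 | 2 | 1 | −16.7 to 33.3 | −66.7 to −16.7 |
| Global health, range 6 | 2 | 1 | −8.3 to 41.7 | −58.3 to −8.3 |
| Fatigue; body image | 3 | 2 | −11.1 to 55.6 | −44.4 to −11.1 |
| Emotional functioning | 4 | 2 | −16.7 to 33.3 | −66.7 to −16.7 |
| Emotional functioning | 4 | 3 | −8.3 to 66.7 | −33.3 to −8.3 |
| Physical functioning | 5 | 3 | −13.3 to 46.7 | −53.3 to −13.3 |
| Physical functioning | 5 | 4 | −6.7 to 73.3 | −26.7 to −6.7 |

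The mean of answered items gives 0 to 100 in every row. The smallest shift is 0.2/3 × 100 = 6.7 points and the largest is 4 × 0.5/3 × 100 = 66.7 points. Scores below zero need answers at or near code 1: one of the 4 possible answers on a two-item scale with range 3, and 4 of the 64 patterns for physical functioning with three answers.

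**Scales exposed.** A single-item scale cannot be partly complete. The multi-item scales are nine of 15 in QLQ-C30 (global health, the five functional scales, fatigue, nausea and vomiting, pain) and four of 23 in QLQ-CR29 (body image, urinary frequency, blood and mucus in stool, stool frequency). That is 13 of 38.

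**The case against.** The strongest reply is that the SAP nowhere says a blank counts as zero. With an item missing, the printed sum is simply undefined, and the surrounding text points away from zero-filling:
- Step 1 calls the raw score an average of the contributing items, which can be read as those answered.
- The 0 to 100 target holds on partial scales only if answered items are averaged.
- The range definition, with the tabulated 3 and 6 and the subtraction of 1, implies a minimum RS of 1, whereas a fixed divisor allows 0.5.
- Protocol 13.3 rules out imputing missing values.

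All of this stands as evidence of intent. It does not repair the text. The section's only definition of n is the full item count, and the sentence on incomplete scales does not change it. Treating the sum as missing whenever an item is missing would contradict the half rule, and averaging answered items departs from the stated n. The scoring manual is cited, but its content is not in the documents, and a printed formula should not depend on an outside source to correct it.

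A reader might infer more: that the plan will certainly bias every partial scale low, and that this will flatter ill subjects at End of Study. The documents do not support that. The bias depends on how the formula is programmed, no item-missing rate is given at any visit, and nothing says partial forms cluster at the end. The downward direction for functional scales also depends on a printed formula that conflicts with the SAP's statement that a higher functional score means better functioning. If that formula were reversed, the same divisor would push functional scores up, to as much as (1 − (0.5 − 1)/3) × 100 = 116.7.

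**Conclusion.** The point holds as an internal conflict in SAP 10.1.1: the stated divisor fails under the SAP's own half rule. Applied literally, with blanks adding nothing to the sum, it moves each partly completed multi-item score by about 6.7 to 66.7 points, downward under the printed formulas, and takes some scores outside 0 to 100. This is more than missing detail, because a divisor is given and it is the wrong one for partial scales.

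The consequence is limited. Only 13 scales are exposed, only when items are skipped, and the skipping rate is unknown, so the effect on any treatment comparison cannot be sized. QLQ-C30 is a secondary outcome and QLQ-CR29 an exploratory one. SAP 5 treats both as supportive, with p-values read descriptively. The primary PFS analysis is not touched. The correction should still be made, because it is free and an individual score can be wrong by two thirds of the scale.

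**What to change.** Replace the definition of n in SAP 10.1.1 with a statement that RS is the sum of the answered items divided by the number of items answered, calculated when at least half of the scale's items are answered and otherwise missing. In practice that means one answer on two-item scales, two on three- and four-item scales, and three on the five-item scale.

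Add a program check that every transformed score lies in 0 to 100. The check supports the corrected definition but cannot replace it, since a score of 33.3 that should be 100 would pass. The direction of the functional-scale formula should be reconciled with the text in the same edit.

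The cost is one sentence in the SAP and a mean of non-missing items in the program. If the program already averages answered items, no result changes.

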10.1.2 EQ-5D-5L

The EQ-5D descriptive system comprises the following 5 dimensions: mobility, self-care, usual activities, pain/discomfort and anxiety/depression. Each dimension has 5 levels: no

problems, slight problems, moderate problems, severe problems, and unable to perform the activity. There will be no imputation of missing data. In addition, the EQ VAS records the respondent's self-rated health on a 20 cm vertical, visual analogue scale with endpoints labelled 0='the best health you can imagine' and 100='the worst health you can imagine'.

10.2 Analysis of QoL Data

For each QLQ-C30 and QLQ-CR29, the summary statistics of absolute scores and changes from baseline will be calculated for the linear transformed score for Global Health status, functional and symptom scale for the Safety Analysis Set.

For Part 2, the study drug and SoC is compared by a 2-sided Wilcoxon rank sum test with the t-Approximation at an alpha of 0.05.

For each of the 5 dimensions of the EQ-5D, tables will be provided to summarize the frequency and percentage of subjects with no, slight, moderate, and severe problems with or were unable to perform each dimension at baseline and end of study. In addition, the shift in the levels of perceived problems at baseline to the levels of perceived response at end of study will be summarized. The EQ VAS and change from baseline will be summarized by study cohort.

All summary tables will be provided for the study cohorts. Data for all subjects will be included in listings.

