7.3.4 Quality of Life

The secondary QoL objective of the study is:

- To compare QoL of subjects who received imalumab in combination with 5-FU/LV or panitumumab versus SoC (investigator choice) as third or fourth treatment line

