10.3.2 Baseline Assessments (Cycle 1 Day 1, Predose)

At the baseline visit (C1D1), subject eligibility will be confirmed and all questionnaires will be completed prior to the start of any assessments. The following baseline assessments will be performed for all subjects prior to dosing:

- EORTC QLQ-C30
- EORTC QLQ-CR29
- EQ-5D
- Vital signs (body temperature, heart rate, blood pressure, respiratory rate, weight, and height; recorded within 30 minutes prior to start of treatment)
- Physical examination
- ECOG PS
- 12-lead ECG
- Clinical laboratory assessments (hematology, serum chemistry, and coagulation). Immediately prior to Cycle 1, laboratory assessments can be performed either on Day -1 or on Day 1 predose
- Urine dipstick test for women of childbearing potential
- Urinalysis
- For subjects receiving imalumab treatment, blood samples for PK (imalumab plasma levels) and PD biomarkers (oxMIF and total MIF) are to be collected **at any time on Day 1 prior to infusion** (see [Table 6](#)).
- Collection of AEs
- Review of concomitant medications/non-drug therapies
- Entry into IRT System for randomization

See the Schedules of Study Procedures and Assessments ([Table 3](#), [Table 4](#), and [Table 5](#)) for additional details on baseline (Day 1, predose) assessments.

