13. STATISTICS

13.1 Sample Size and Power Calculations

The final sample size of the Safety Run-in (Part 1) is dependent on the pre-stated rules for dose escalation (see Section 8.2.1). In Part 1, the sample size for each dosing regimen (ie, imalumab + 5-FU/LV and imalumab + panitumumab) is expected to be between 6 and 12 subjects (ie, 3 to 6 subjects at each imalumab dose level). Non-evaluable subjects will be replaced to meet study objectives.

The sample size of the exploratory Phase 2a (Part 2) is estimated to be a total of 66 subjects. Assuming that the median PFS is 2.4 months in the control arm and 4.25 months in the experimental arm (hazard ratio 0.565), and using a one-sided α of 0.15 and β of 0.20 with a drop-out rate of 20% at 6 months, 48 PFS events are needed. With an enrollment ratio of 2:1, and taking into account the time for accrual of 1 year and an additional follow-up period of 6 months after the last subject is enrolled, the sample size needed is a total of 44 subjects in the imalumab-containing treatment arms and 22 subjects in the control arm (SoC), for a total of 66 subjects.

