5.3 Definition of Baseline

Baseline will be defined as the last assessment before the date and time of first administration (C1D1) of imalumab or SoC. For subjects who have not received any study drug, the baseline will be the last assessment performed at Screening, Baseline, or C1D1.

If more than one baseline scan is recorded then measurements from the one that is closest and prior to the date of randomization will be used to define the baseline.

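### The Part 2 quality-of-life test does not adjust for the baseline score as a covariate and names neither the variable nor the visit tested, so it gives up precision that data already planned could supply

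*SAP*

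**What the plan says.** Protocol 7.3.4 makes the QoL comparison a secondary objective: "To compare QoL of subjects who received imalumab in combination with 5-FU/LV or panitumumab versus SoC". Protocol 8.4.2.5 measures it with the QLQ-C30. The QLQ-CR29 and EQ-5D are exploratory (Protocol 8.4.3).

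Protocol 10.3.2 schedules the questionnaires on Cycle 1 Day 1 and puts them first: "all questionnaires will be completed prior to the start of any assessments". The list that contains them opens with "The following baseline assessments will be performed for all subjects prior to dosing". SAP 5.3 then fixes the baseline value: "Baseline will be defined as the last assessment before the date and time of first administration (C1D1) of imalumab or SoC". After baseline, Protocol Tables 3 to 5 schedule the questionnaires only at the End of Study/Early Termination and Safety Follow-Up visits.

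For the QLQ scales, SAP 10.2 says "the summary statistics of absolute scores and changes from baseline will be calculated for the linear transformed score". The between-arm test follows: "For Part 2, the study drug and SoC is compared by a 2-sided Wilcoxon rank sum test with the t-Approximation at an alpha of 0.05". That sentence gives no covariate, strata, analysis variable or visit. SAP 11.2 refers back to 10.1 and 10.2, and SAP 5 adds no QoL model.

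**The concern.** A rank sum test on one number per subject does not condition on where the subject started. With 44 against 22 subjects, a modest chance difference in baseline QoL is to be expected, and part of it enters the result whichever variable is tested. On absolute scores the arm that started better tends to look better. On changes, regression to the mean makes the arm that started better look worse. In either case, variation that baseline could explain stays in the residual.

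Because the analysis variable is not stated, two programmers could follow SAP 10.2 correctly and run tests with different variances and opposite sensitivity to a baseline imbalance. At stake is the precision and reproducibility of a secondary comparison, not the primary result.

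**Working it through.** **Inputs from the documents.** Part 2 size, Protocol 13.1: "a total of 44 subjects in the imalumab-containing treatment arms and 22 subjects in the control arm (SoC), for a total of 66 subjects". Test: two-sided, alpha 0.05 (SAP 10.2).

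**Inputs assumed, because the documents give none.** Baseline to follow-up correlation rho = 0.5, with 0.3 and 0.7 shown. Standardised effect d from 0.2 to 1.0 SD. Continuous normal scores with equal SD at both times. All 66 subjects contribute. Efficiency of a rank test relative to a t test 3/pi = 0.955.

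**The plan's own figure.** No power is stated for QoL; the 66 comes from PFS. One-sided alpha 0.15, 80% power, HR 0.565 and 2:1 allocation give (1.036 + 0.842)² / [(2/9) × (ln 0.565)²] = 48.7, so 49 events against the stated 48. At 48 events the power is 79.6%. The stated figure reproduces to within one event.

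**Effect of a chance baseline difference.** The standard error of a difference in means is sqrt(1/44 + 1/22) = 0.261 SD. A baseline difference of 0.25 SD is 0.25/0.261 = 0.96 standard errors (two-sided p about 0.34), so it would be unremarkable. If the arms differ by D at baseline:
- absolute follow-up scores carry rho × D, which is +0.125 SD for D = 0.25 and rho = 0.5;
- changes carry -(1-rho) × D, which is -0.125 SD in the same case.

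**Variance, relative to the follow-up score.** Absolute: 1. Change: 2(1-rho). Baseline-adjusted: 1-rho². The adjusted variance is the smallest of the three for any rho strictly between 0 and 1. At rho = 0.5 the values are 1, 1 and 0.75, so the loss is then the same for absolute scores and for changes.

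**Power.** Power = Phi(d × sqrt(3/pi) / (0.261 × f) - 1.96), where f is the square root of the relative variance. At d = 0.7 and rho = 0.5:
- unadjusted: 0.7 × 0.977 / 0.261 = 2.62, and Phi(0.66) = 74.5%;
- adjusted: 2.62 / sqrt(0.75) = 3.02, and Phi(1.06) = 85.7%.

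All results at rho = 0.5, 44 versus 22:

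| d (SD) | Unadjusted | Adjusted | Gain (points) |
|---|---|---|---|
| 0.2 | 11.3% | 13.7% | 2.4 |
| 0.3 | 20.1% | 25.3% | 5.2 |
| 0.5 | 46.5% | 58.0% | 11.5 |
| 0.6 | 61.2% | 73.7% | 12.4 |
| 0.7 | 74.5% | 85.7% | 11.1 |
| 0.8 | 84.9% | 93.3% | 8.3 |
| 1.0 | 96.3% | 99.1% | 2.8 |

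Gains are taken before rounding. A simulation of bivariate normal scores put rank ANCOVA about 9 to 12 points ahead of the Wilcoxon test at rho = 0.5.

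**Other correlations, d = 0.7.**

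| rho | Wilcoxon, absolute | Wilcoxon, change | Adjusted |
|---|---|---|---|
| 0.3 | 74.5% | 60.0% | 78.4% |
| 0.5 | 74.5% | 74.5% | 85.7% |
| 0.7 | 74.5% | 92.2% | 95.6% |

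The gain is about 4 points for absolute scores at rho = 0.3 and about 3 for changes at rho = 0.7. In the opposite pairings it is 18 and 21 points. The size depends heavily on the variable that SAP 10.2 leaves open.

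**Fewer questionnaires.** With an illustrative 32 versus 16 subjects, d = 0.7 and rho = 0.5, power is 60.8% unadjusted and 73.2% adjusted. The levels fall; the gap stays similar (12.4 points).

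**The case against.** The strongest case against is that nothing here is wrong. The unadjusted Wilcoxon test is valid under randomisation. SAP 5 treats all secondary and exploratory tests as supportive, with p-values read descriptively, and no QoL power or decision rule depends on them. All of that stands.

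A rank test also suits these scales. By SAP Tables 6 and 7, 25 of the 38 scales are single items with four possible answers. The normal model and the 0.955 efficiency are therefore approximations, and heavy ties could move the power figures. This stands too, and it favours a rank-based adjustment over relying on ANCOVA alone.

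The power levels assume that all 66 subjects give a follow-up questionnaire. The analysis cut-off is at 48 PFS events (Protocol 13.5), post-baseline questionnaires come only when a subject leaves treatment or afterwards, and only available data are used (Protocol 13.3). The levels are therefore optimistic.

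A reader might infer that the test ignores baseline altogether. The documents do not support that: SAP 10.2 calculates changes from baseline, and if those are what is tested, baseline enters by subtraction. A reader might also infer that a chance imbalance passes in full into absolute scores. That would need rho = 1; the share carried is rho.

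**Conclusion.** The point holds as one of efficiency and specification. SAP 10.2 has no baseline covariate in its between-arm QoL test and leaves the analysed variable and visit open, although the baseline score is due from every subject. The direction is secure: for any rho strictly between 0 and 1, adjustment has lower variance than either variable the test might use.

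The size is conditional. The gain of 8 to 12 points needs rho near 0.5, effects of 0.5 to 0.8 SD and near-normal scores; the power levels also need all 66 subjects contributing. It should not be quoted as a general loss, because the documents give neither the correlation nor the effect size and the gain is much smaller in parts of the plausible range. Nothing in the documents makes the planned test invalid or any stated figure wrong. This is a worthwhile improvement, not a necessary correction.

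**What to change.** In SAP 10.2:

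1. Name the analysed visit. End of Study/Early Termination is a natural choice, since 10.2 already uses end of study for the EQ-5D tables.
2. State that the post-baseline score is the analysed variable and make the between-arm test a rank analysis of covariance. Rank the post-baseline and baseline scores over both arms, regress the first set of ranks on the second, and compare the residuals between arms.
3. Report the baseline-adjusted mean difference with its 95% CI from an ANCOVA with the baseline score as covariate. Section 10.2 currently plans no between-arm estimate.
4. Keep the unadjusted Wilcoxon test as supportive, on the same variable and visit.

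The cost is a few sentences in the SAP and a few lines of SAS, with no new data collection. One small downside is that subjects without a baseline questionnaire drop out of the adjusted analysis, as they would from any analysis of changes. Adjustment does not deal with the timing of the post-baseline questionnaires, which is a separate matter.
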